- 24. To include color, appearance, glucose, bilirubin, ketone, specific gravity, blood, pH, protein, urobilinogen, nitrite, leukocyte esterase. If warranted by dipstick analysis, microscopic analysis to include RBC, WBC, casts, crystals, epithelial cells, and bacteria. Will be performed at screening, and when clinically indicated.
- 25. For POCBPs only.
- 26. CA19-9 will be measured from blood collected at screening (post-operative measurement required within 3 weeks of C1D1), C1D1, during PK sampling, on days of BNT321 administration and at disease assessment time points detailed in Footnote 25. During BNT321 monotherapy every 3 months (12 weeks), every 2 years (±7 days), and then every 6 months for 3 years. For all collections on BNT321 administration days, blood will be collected both pre-infusion and post-infusion (end of infusion [EoI] +5 min [± 5 min]). For further details, refer to Table 3.
- 27. For a full pharmacokinetic profile and in-depth sampling, blood will be collected on C2D3 and C3D3, (pre-infusion, EoI +5 min] ± 5 min], EoI +1 h [±15 min] and EoI +4 h [±30 min]). For Cycles 4 onwards, only C_{trough} (pre-infusion) and C_{max} (EoI +5 min [±5 min]) will be drawn on day of BNT321 administration. All other timepoints will include only one blood draw timepoint per day. For further details, refer to Table 3.
- 28. Disease assessment will consist of imaging by CT/MRI scan and serum CA19-9 and will be performed at screening (baseline post-operative imaging within 4 weeks of C1D1 and serum CA19-9 within 3 weeks of C1D1 are required), and then after C1D1 every 3 months (12 weeks) for 2 years and then every 6 months for 3 years (±7 days). CT with contrast or MRI (as appropriate for patient, or multiparametric MRI following an inconclusive CT). Patients should be evaluated with the same imaging method (CT or MRI) throughout the trial.
- 29. Anti-drug antibodies will be measured from blood collected prior to dosing of mFOLFIRINOX on C1D1, C3D1, C6D1, and at EOT.
- 30. ADCC, CDC and cytokines will be measured from blood collected prior to dosing of mFOLFIRINOX and/or BNT321 on days of trial drug administration. Collected on the following days: C1D1, C2D3, C2D8, C4D3, C4D8, C16D1 and C16D5. For Cycle 4 collections, should be adjusted to C4D1 and C4D5 if BNT321 administration is given on C4D1. Whole blood collected for PBMC isolation for ADCC assessment will only be collected if logistically manageable.
- 31. FFPE tumor tissue from surgical resection is required during screening. In the event of progression, if a biopsy is performed, a sample (optional) should be requested.
- 32. For ctDNA assessment, blood will be collected at C1D1, C6D1, C18D1, and at time of progression. Additional information on sample submission is included in the laboratory manuals.
- 33. Randomization should be done between Day -3 and C1D1.

ical Trial Protocol Page 19 of 127

BNT321-02 Version: 2.0

Date: 22 JAN 2024

- 34. BNT321 in randomized Phase II part of this trial will be administered following the completion of the 5-FU infusion (i.e., on Day 3 of each cycle from Cycle 2 onwards and on Day 1 during the monotherapy part of the protocol, as per Footnote 3). Day 1 administration of BNT321 may be utilized throughout the Phase II part of the trial, following review of Phase I safety data and alignment with the SRC.
- 35. mFOLFIRINOX will be administered as per Section 6.1.

Abbreviations: ADCC = antibody-dependent cell-mediated cytotoxicity; ALT = alanine aminotransferase; AST = aspartate aminotransferase; CnDn = cycle number day number; CA19-9 = sialyl-Lewis A (sLe^a) antigen; CDC = complement-dependent cytotoxicity; CT = computed tomography; ctDNA = circulating tumor DNA; d = days; DFS = disease-free survival; DPD = dihydropyrimidine dehydrogenase; ECG = electrocardiogram; ECOG = Eastern Cooperative Oncology Group; Eol = end of infusion; EOT = end of treatment; 5FU = 5-flourouracil; FFPE = formalin-fixed paraffin-embedded tissue; FU = follow-up; GGT = gamma-glutamyl transferase; h = hours; HGB = hemoglobin; HCT = hematocrit; HRQoL = health-related quality of life; IHC = immunohistochemistry; KPS = Karnofsky performance status; min = minutes; MCH = mean corpuscular hemoglobin; MCV = mean corpuscular volume; MRI = magnetic resonance imaging; PDAC = pancreatic adenocarcinoma; PK = pharmacokinetics; POCBP = patient of childbearing potential; RBC = red blood cell; SCR = screening; SRC = safety review committee; TB = tuberculosis; t_{max} = time required to reach C_{max}; UGT1A1 = UDP glucuronosyltransferase family 1 member A1; WBC = white blood cell.

Page 20 of 127 Version: 2.0 Date: 22 JAN 2024

Table 3: Supplementary table for PK – Phase I and Randomized Phase II - combination arm (mFOLFIRINOX + BNT321)

		Cycle 1			Cycle 2-	-3			Су	rcle 4–24	
Assessment for Phase I	SCR	D 4	Day of BNT321 administration						Day of BNT321 administration		
	0,	Day 1	Predose	Eol +5 min [±5 min]	Eol +30 min [±5 min]	Eol +1 h [±5 min]	Eol +4 h [±30 min]	Day 8	Predose	Eol +5 min [±5 min]	
Blood sample for BNT321 pharmacokinetics			х	Х	х	х	Х	Х	х	х	
Blood sample for CA19-9	Х	Х	Х	Х				X*	Х	Х	

Assessment for Randomized Phase II-		Cycle 1			Cycle 2-	3			Су	rcle 4–24
combination arm only (mFOLFIRINOX + BNT321)	SCR			Day o	of BNT321 adminis	stration		_	Day of BNT321 administration	
	0,	Day 1	Predose	Eol +5 min [±5 min]	Eol +30 min [±5 min]	Eol +1 h [±5 min]	Eol +4 h [±30 min]	Day 8	Predose	Eol +5 min [±5 min]
Blood sample for BNT321 pharmacokinetics			х	Х		х	х	X*	X**	X**
Blood sample for CA19-9	Χ	Х	Х	Х				X*	X**	X**

Eol = end of infusion; min = minutes; h = hours; SCR = screening.

^{* =} only on Cycle 2; ** = every fourth cycle (e.g Cycle 4, Cycle 8, Cycle 12 etc.)

Page 21 of 127 Version: 2.0 Date: 22 JAN 2024

Table 4: Schedule of activities and procedures – Randomized Phase II; control arm (mFOLFIRINOX)

Treatment cycle (14 d)	SCR 2	Cycle 1		Cycle 2		Су	rcle 3	(Cycle 4-12	!	EOT 3	Safety FU 4	Survival FU ⁵
Days ¹		1	1	3	8	1	3	1	3	8		Š	Su
Informed consent ⁶	X												
Eligibility	X												
Medical history 7	X												1
TB screening ⁸	X												
DPD deficiency screening ⁹	X												
UGT1A1 mutation screening ¹⁰	Х												
Demographics	Х												
Height	Х												
Weight ¹¹	Х	Х	Х			Х		Х			Х		
Physical examination	Х												
Symptom-directed exam 12		Х	X	[X]	[X]	X	[X]	Х	[X]	[X]	X		1
Vital signs ¹³	X	Х	X	X	X	X	Х	Х	X	X	X	X	1
Performance status 14	X	Х	Х			Х		Х			Х		
HRQoL ¹⁵	Х					X		[X]			X		X
Concomitant medications 16	Х	Х	X	Х	Х	X	Х	Х	Х	Х	X	X	
Adverse events 17		Х	X	Х	Х	X	Х	Х	Х	Х	X	X	
ECGs 18	Х	X	X			X		[X]			Х		
Hematology 19	Х	Х	X			X		Х			X	X	
Chemistry ²⁰	Х	Х	X			X		Х			X	X	
Serum amylase ²¹		X	Х			Х		Х			Х		

Page 22 of 127 Version: 2.0 Date: 22 JAN 2024

Treatment cycle (14 d)	SCR 2	SCR 2	SCR 2	Cycle 1		Cycle 2		Су	rcle 3	(Cycle 4-12		EOT 3	Safety FU 4	Survival FU ⁵
Days ¹		1	1	3	8	1	3	1	3	8	1	ű	Su		
Serum lipase ²¹		X	Х			Х		Х			X				
Haptoglobin ²¹		Х	Х			Х		Х			X				
GGT ²²	Х	Х	Х			X		Х			Х				
Urinalysis ²³	Х														
Urine pregnancy test 24	Х	Х	Х			Х		Х			X				
CA19-9 ²⁵	Х	Х		Х	X		Х	[X]**	X**		X		Х		
Disease assessment ²⁶	Х							Х			Х		X		
ADCC, CDC, and cytokines ²⁷		Х		Х	Х				X	X					
Tumor biopsy ²⁸	Х										[X]				
ctDNA ²⁹		Х						[X]			X		[X]		
Randomization ³⁰	X 30														
mFOLFIRINOX administration 31		Х	Х			Х		Х							
Survival status ⁵													Х		

X - Required, [X] - Optional, or not with every visit

- 1. Window for all procedures, except those performed on Day 3 of all cycles, is ±3 days of the scheduled day. Day 3 procedures are performed without window.
- 2. Screening visit performed within 21 days prior to Cycle 1 Day 1 and may be repeated within 7 days of C1D1 if requested by Medical Monitor (e.g., borderline eligibility or clinical instability).
- 3. End of treatment (EOT) visit will be performed at Week 25 or on the day the decision is made to discontinue mFOLFIRINOX.
- 4. Safety FU visit is performed 28 days (±14 days) after last dose of mFOLFIRINOX. EOT and safety FU visits may be combined for patients who discontinue mFOLFIRONOX outside of a clinic visit or who had no Grade 2 or higher toxicity at their last trial visit.

^{** -} Every fourth cycle (e.g., Cycle 4, Cycle 8, Cycle 12 etc.)

Clinical Trial Protocol BNT321-02 Page 23 of 127 Version: 2.0 Date: 22 JAN 2024

- 5. Survival FU visits will include Week 35 for ctDNA and Week 48 for disease assessment and ctDNA. Survival FU will begin 12 weeks (±30 days) after safety FU until 5 years after C1D1. DFS status will be recorded every 3 months for 2 years and then every 6 months for the next 3 years. All patients will be contacted, or the medical records reviewed to report survival status, disease progression and to provide an update on CA19-9 and tumor imaging. Initiation of any additional therapy for pancreatic cancer will be documented.
- 6. Informed consent will be obtained prior to performing any trial-specific screening procedures.
- 7. Medical history should include but not limited to lifetime history of cancer, tumor characteristics such as mutation status, cancer-related somatic genomic alterations and germline status, prior non-cancer significant medical conditions for the 2 years prior to trial entry, other clinically relevant diseases, surgeries, use of alcohol and/or drugs abuse and reproductive status.
- 8. For patients whom the treating physician considers to be at increased risk for infection, in which case testing should be done according to institutional practice standards at screening.
- 9. DPD testing to be done at screening if required by local regulations.
- 10. UGT1A1 testing at screening if required by local regulations.
- 11. Obtained at screening, Day 1 of every cycle, and EOT, may be reduced to every other cycle based on investigator's discretion.
- 12. Symptom-directed physical examinations will be performed on Day 1 of each cycle prior to treatment administration and at any visit where the patient indicates new symptoms that require evaluation or based on investigator's discretion.
- 13. Vital signs e.g., blood pressure, body temperature, heart rate, and respiratory rate will be performed prior to start of infusion. On non-treatment visits, vital signs will be performed once. Vital signs will also be performed at the safety FU visit.
- 14. Performance status must be recorded as ECOG and will be performed at screening and Day 1 of every cycle, at EOT, and as needed according to investigator's discretion based on new symptoms and/or medical concerns. Refer to the Appendix 1 for conversion between ECOG and KPS.
- 15. HRQoL will be performed at screening, Day 1 of every other treatment cycle starting from Cycle 3 to 12, at EOT and at every disease assessment (see Footnote 26 for timing of disease assessments).
- 16. Recorded from 21 days prior to the first administration of mFOLFIRINOX to EOT or safety FU visits. Includes prescription medications, over-the-counter medications, and supplements.
- 17. Adverse events will be collected and reported from the signing of the trial-specific ICF until safety FU.
- 18. ECGs will be performed at screening and on Day 1 of every cycle for C1 through C3. On these days ECGs are obtained prior to treatment, at t_{max}, and at end of last mFOLFIRINOX infusion. Investigators may obtain ECGs at additional timepoints in Cycle 4 to 12 if indicated based on results in Cycle 1 to 3. ECGs will also be obtained prior to first BNT321 administration on Cycle 13, and at EOT and as clinically indicated during BNT321 monotherapy per assessment of the trial investigator. ECGs are performed as triplicate exams at all study timepoints per Section 8.3.3.
- 19. Complete blood count (CBC) with differential to include WBC, RBC, HGB, HCT, platelets, MCV, and MCH to be performed at screening, Day 1 of every cycle, Week 25/EOT, at safety FU visit, and as needed according to investigator's discretion based on new symptoms and/or medical concerns.
- 20. Blood chemistry to include sodium, potassium, chloride, bicarbonate, blood urea nitrogen, creatinine, glucose, calcium, phosphate, magnesium, AST, ALT, total bilirubin, alkaline phosphatase, total protein, albumin, and uric acid to be performed at screening, Day 1 of every cycle, Week 25/EOT, at safety FU visit, and as needed according to investigator's discretion based on new symptoms and/or medical concerns.
- 21. Serum amylase, lipase and haptoglobin will be performed on Day 1 of every cycle, Week 25/EOT, and as needed according to investigator's discretion based on new symptoms and/or medical concerns.

Page 24 of 127 Version: 2.0 Date: 22 JAN 2024

- 22. GGT will be performed at screening and on Day 1 of every cycle, Week 25/EOT, and as needed according to investigator's discretion based on new symptoms and/or medical concerns.
- 23. To include color, appearance, glucose, bilirubin, ketone, specific gravity, blood, pH, protein, urobilinogen, nitrite, leukocyte esterase. If warranted by dipstick analysis, microscopic analysis to include RBC, WBC, casts, crystals, epithelial cells, and bacteria. Will be performed at screening, and when clinically indicated.
- 24. For POCBPs only.
- 25. CA19-9 will be measured from blood collected at screening (post-operative measurement required within 3 weeks of C1D1), C1D1, at EOT and at disease assessment timepoints detailed in Footnote 23.
- 26. Disease assessment will consist of imaging by CT/MRI scan and serum CA19-9 and will be performed at screening (baseline post-operative imaging within 4 weeks of C1D1 and serum CA19-9 within 3 weeks of C1D1 are required), and then after C1D1 every 3 months (12 weeks) for 2 years, and then every 6 months for 3 years (±7 days). CT with contrast or MRI (as appropriate for patient, or multiparametric MRI following an inconclusive CT). Patients should be evaluated with the same imaging method (CT or MRI) throughout the trial.
- 27. ADCC, CDC and cytokines will be measured from blood collected prior to dosing of mFOLFIRINOX. Collected on the following days: C1D1, C2D3, C2D8, C4D3, and C4D8. Whole blood collected for PBMC isolation for ADCC assessment will only be collected if logistically manageable.
- 28. FFPE tumor tissue from surgical resection is required during screening. In the event of progression, if a biopsy is performed, a sample (optional) should be requested.
- 29. For ctDNA assessment, blood will be collected at C1D1, C6D1, Week 35, Week 48, EOT visit and at time of progression, if applicable. Additional information on sample submission is included in the laboratory manuals.
- 30. Randomization should be done between Day -3 and C1D1.
- 31. mFOLFIRINOX will be administered as per Section 6.1.

Abbreviations: ADCC = antibody-dependent cell-mediated cytotoxicity; ALT = alanine aminotransferase; AST = aspartate aminotransferase; CnDn = cycle number day number; CA19-9 = sialyl-Lewis A (sLe^a) antigen; CDC = complement-dependent cytotoxicity; CT = computed tomography; ctDNA = circulating tumor DNA; d = days; DFS = disease-free survival; DPD = dihydropyrimidine dehydrogenase; ECG = electrocardiogram; ECOG = Eastern Cooperative Oncology Group; EOT = end of treatment; 5FU = 5-flourouracil; FFPE = formalin-fixed paraffin-embedded tissue; FU = follow-up; GGT = gamma-glutamyl transferase; h = hours; HGB = hemoglobin; HCT = hematocrit; HRQoL = health-related quality of life; IHC = immunohistochemistry; KPS = Karnofsky performance status; min = minutes; MCH = mean corpuscular hemoglobin; MCV = mean corpuscular volume; MRI = magnetic resonance imaging; PDAC = pancreatic adenocarcinoma; PK = pharmacokinetics; POCBP = patient of childbearing potential; RBC = red blood cell; SCR = screening; TB = tuberculosis; t_{max} = time required to reach C_{max}; UGT1A1 = UDP glucuronosyltransferase family 1 member A1; WBC = white blood cell.

Page 25 of 127 Version: 2.0 Date: 22 JAN 2024

TABLE OF CONTENTS

1	PROTOCOL SUMMARY	2
1.1	Synopsis	2
1.2	Schema	8
1.3	Schedule of activities	9
TABLE C	F CONTENTS	25
LIST OF	TABLES	29
LIST OF	FIGURES	29
ABBREV	IATIONS/TERMS	30
2	INTRODUCTION	32
2.1	Trial rationale	32
2.2	Background	32
2.2.1	Medical need	33
2.2.2	Introduction to the investigational medicinal product	34
2.3	Benefit/risk assessment	35
2.3.1	Benefit assessment	35
2.3.2	Risk assessment and mitigation strategy	36
2.3.3	Overall benefit/risk conclusion	40
3	OBJECTIVES AND ENDPOINTS	40
4	TRIAL DESIGN	43
4.1	Overall design	43
4.1.1	Dose escalation (Phase I)	44
4.1.2	Randomized mFOLFIRINOX ± BNT321 (Phase II)	44
4.1.3	Adaptive trial design elements	44
4.1.4	Duration of the trial periods	45
4.1.5	Planned number of patients	45
4.2	Rationale for the trial design	46
4.2.1	Trial design rationale for Phase I: Dose escalation	46
4.2.2	Trial design rationale for Phase II: Randomized mFOLFIRINOX ± BNT321	47
4.2.3	Contraception and pregnancy testing	47

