Demographics	Х													
TB screening ⁹	Х													
DPD deficiency screening ¹⁰	X													
UGT1A1 mutation screening 11	X													
Height	X													
Weight ¹²	X	Х	Х			X		Х			Х	Х		
Physical examination	X											Х		
Symptom-directed exam ¹³		Х	Х	[X]	[X]	Х	[X]	Х	[X]	[X]	Х			
Vital signs ¹⁴	X	X	Х	Х	Х	Х	Х	Х	Х	Х	Х	Х	Х	
Performance status 15	X	X	X			Х		Х			Х	Х		
HRQoL ¹⁶	X					Х		[X]			[X]	Х		Х
Concomitant medications 17	X	Х	Х	Х	Х	Х	Х	Х	X	Х	Х	Х	Х	
Adverse events 18		Х	Х	Х	Х	Х	X	Х	Х	Х	Х	Х	Х	
ECGs 19	X	Х	Х			Х		[X]				Х		
Hematology ²⁰	X	Х	Х			Х		Х			Х	Х	Х	
Chemistry ²¹	X	Х	Х			Х		Х			Х	Х	Х	

Page 16 of 127 Version: 2.0 Date: 22 JAN 2024

Treatment cycle (14 d)	SCR 2	Cycle 1		Cycle 2	2	су	cle 3	c	ycle 4-12		BNT321 monotherapy Cycle 13-24 ³	EOT 4	Safety FU ⁵	Survival FU 6
Days ¹		1	1	3	8	1	3	1	3	8	1			S
Serum amylase 22		Х	Х			Х		Х			Х	Х		
Serum lipase ²²		Х	Χ			Х		Х			Х	Х		
Haptoglobin ²²		Х	Х			Х		Х			Х	X		
GGT ²³	Х	Х	Х			Х		Х			Х	X		
Urinalysis ²⁴	Х													
Urine pregnancy test ²⁵	Х	Х	Х			X		Х			Х	X		
CA19-9 ²⁶	Х	Х		Х	Х		Х	[X]**	X**		X**	Х		Х
Pharmacokinetics 27				X	Х		Х	[X]**	X**		X**			
Disease assessment 28	Х							Х			Х	Х		X
Anti-drug antibody ²⁹		Х				Х		[X]				Х		
ADCC, CDC, and cytokines 30		X		X	Х				Х	X	Х			
Tumor biopsy ³¹	Х											[X]		
ctDNA 32		Х						[X]			Х	Х		
Randomization ³³	X 33													
BNT321 administration ³⁴				Х			Х		X		Х			
mFOLFIRINOX administration 35		Х	Х			Х		Х						
Survival status ⁶														Х

X - Required, [X] - Optional, or not with every visit

^{** -} Every fourth cycle (e.g., Cycle 4, Cycle 8, Cycle 12 etc.)

Clinical Trial Protocol BNT321-02

BioNTech SE Confidential

Version: 2.0 Date: 22 JAN 2024

Page 17 of 127

- 1. Window for all procedures, except those performed on Day 3 of all cycles, is ±3 days of the scheduled day. Day 3 procedures are performed without window.
- 2. Screening visit performed within 21 days prior to Cycle 1 Day 1 and may be repeated within 7 days of C1D1 if requested by Medical Monitor (e.g., borderline eligibility or clinical instability).
- 3. BNT321 monotherapy will continue every two weeks on Day 1 of every cycle for an additional 12 cycles to complete the adjuvant therapy course.
- 4. End of treatment (EOT) visit will be performed on the day the decision is made to discontinue BNT321 administration or at the completion of 24 cycles of therapy.

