- 5. Safety FU visit is performed 28 days (±14 days) after last dose of BNT321. EOT and safety FU visits may be combined for patients who discontinue BNT321 outside of a clinic visit or who had no Grade 2 or higher toxicity at their last trial visit.
- 6. Survival FU visits will be performed beginning 12 weeks (±30 days) after safety FU until 5 years after C1D1. DFS status will be recorded every 3 months for 2 years and then every 6 months for the next 3 years. All patients will be contacted, or the medical records reviewed to report survival status, disease progression and to provide an update on CA 19-9 and tumor imaging. Initiation of any additional therapy for pancreatic cancer will be documented.
- 7. Informed consent will be obtained prior to performing any trial-specific screening procedures.
- 8. Medical history should include but not limited to lifetime history of cancer, tumor characteristics such as mutation status, cancer-related somatic genomic alterations and germline status, prior non-cancer significant medical conditions for the 2 years prior to trial entry, other clinically relevant diseases, including tuberculosis, surgeries, use of alcohol and/or drugs abuse and reproductive status.
- 9. For patients whom the treating physician considers to be at increased risk for infection, in which case testing should be done according to institutional practice standards at screening.
- 10. DPD testing to be done at screening if required by local regulations.
- 11. UGT1A1 testing at screening if required by local regulations.
- 12. Obtained at screening. Day 1 of every cycle and EOT, may be reduced to every other cycle based on investigator's discretion.
- 13. Symptom-directed physical examinations will be performed on Day 1 of each cycle prior to treatment administration and at any visit where the patient indicates new symptoms that require evaluation or based on investigator's discretion.
- 14. Vital signs e.g., blood pressure, body temperature, heart rate, and respiratory rate will be recorded on each designated visit days and prior to and approximately every 30 minutes until at least 2 h after completion of BNT321 infusion. On mFOLFIRINOX treatment visits, vital signs will be performed prior to start of infusion. On nontreatment visits, vital signs will be performed once. Vital signs will also be performed at the safety FU visit.

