8.4.1 Time period and frequency for collecting AE and SAE information

All AEs/SAEs will be collected from the signing of the ICF until the safety follow-up visit at the time points specified in the SoA (Section 1.3).

Medical occurrences that begin before the start of trial treatment administration but after obtaining informed consent will be recorded on the respective Medical History/Current Medical Conditions section of the eCRF and not in the AE section.

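### The footnotes that let the end-of-treatment and safety follow-up visits be combined do not date the combined visit, so a site can follow the protocol and still close adverse-event collection before the 28 ±14 day safety window opens.

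*Combined protocol and SAP*

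**What the plan says.** Four rules in the protocol bear on this.

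- **Safety follow-up date.** Table 2 footnote 5: "Safety FU visit is performed 28 days (±14 days) after last dose of BNT321". Table 1 footnote 5 has the same timing. Table 4 footnote 4 uses it for the control arm, counted from the last mFOLFIRINOX dose.
- **Permission to combine.** The same footnotes give two routes to a single visit. The first: "EOT and safety FU visits may be combined for patients who discontinue BNT321 outside of a clinic visit". The second covers anyone whose most recent visit showed nothing worse than Grade 1 toxicity. Apart from the drug named, the wording is the same in Tables 1, 2 and 4.
- **EOT date.** In the BNT321 schedules the EOT "visit will be performed on the day the decision is made to discontinue BNT321 administration or at the completion of 24 cycles". In the control schedule: "End of treatment (EOT) visit will be performed at Week 25 or on the day the decision is made to discontinue mFOLFIRINOX".
- **End of AE collection.** Section 8.4.1: "All AEs/SAEs will be collected from the signing of the ICF until the safety follow-up visit". The AE footnotes to the three schedules agree, and the AE row has no mark under survival follow-up.

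Two analysis definitions depend on this collection period. Section 9.5.4 counts AEs as treatment-emergent up to 28 days after the last IMP dose, and Section 10.4.1 up to 60 days. After those limits only events assessed as related count.

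**The concern.** The footnotes permit one visit in place of two but do not say whether it takes the EOT date or must stay between days 14 and 42. Because AE collection closes at safety follow-up, the choice of date decides how long a patient is observed after the last dose.

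The two triggers point different ways. Stopping outside a clinic visit fits an EOT visit postponed to the safety window. Having no Grade 2 or higher toxicity reads more naturally as excusing the patient from the later visit. Sites can reasonably diverge, and under the second trigger the length of observation depends on observed toxicity.

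AEs are a primary endpoint in Phase I and a secondary endpoint in Phase II. Merging also reduces two required sets of hematology, chemistry and vital signs (EOT and safety follow-up) to one. That matters because the known BNT321 signal is hepatic: the three dose-limiting toxicities reported for the earlier combination cohort (Section 2.3.2) all involved transaminase elevations. A symptom-free rise has to be measured to be found.

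**Working it through.** The plan states no figure on this point, so the check is calendar arithmetic followed by a comparison of the collection period with the analysis windows.

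**Inputs.** 14-day cycles; 12 chemotherapy cycles in the control arm, 24 cycles in the combination arm with BNT321 on Day 1 in Cycles 13–24; control EOT at Week 25; safety visit at 28 ±14 days; treatment-emergent limits of 28 days (Section 9.5.4) and 60 days (Section 10.4.1).

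**Step 1: permitted safety window.** 28 − 14 = day 14 to 28 + 14 = day 42 after the last dose.

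**Step 2: where EOT falls for completers.** The day number of Cycle k Day 1 is 14 × (k − 1) + 1.

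- Control: Cycle 12 Day 1 = 14 × 11 + 1 = day 155. Week 25 starts on 24 × 7 + 1 = day 169. The gap is 169 − 155 = 14 days from the start of the last infusion, at the lower edge of the window.
- Combination: Cycle 24 Day 1 = 14 × 23 + 1 = day 323. Cycle 24 ends on day 336. Depending on how completion of 24 cycles is read, EOT falls 0 to 336 − 323 = 13 days after the last dose, before the window opens.
- Early stoppers, either arm: EOT is the decision day. With two-weekly dosing this is typically 0 to about 14 days after the last dose, and it can be later.

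**Step 3: share of the treatment-emergent window left unobserved.** If collection closes g days after the last dose, the share is max(0, W − g)/W.

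| Collection closes on day g | W = 28 | W = 60 |
|---|---|---|
| 0 | 28/28 = 100% | 60/60 = 100% |
| 14 | 14/28 = 50% | 46/60 = 77% |
| 28 | 0% | 32/60 = 53% |
| 42 | 0% | 18/60 = 30% |

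An unmerged visit on day 14 already complies, so the 50% in that row is not caused by merging. A merge on day 0 adds 100 − 50 = 50 percentage points against the earliest compliant unmerged visit, and 100 points against a visit on the nominal day 28.

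**Step 4: what catches events after collection closes.**

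- Sections 10.4.2.2 and 10.4.4 keep later events reportable only where a relationship is suspected.
- Section 8.4.2 does not oblige investigators to look for events after trial participation has concluded.
- Survival follow-up starts 12 weeks (±30 days) after safety follow-up. It covers survival, progression, CA19-9, imaging and new therapy, not AEs.

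**Step 5: scale, on assumed inputs.** The documents give neither merge shares nor post-treatment event rates. Assume a risk p of a new AE within 28 days of 5% to 20%, a merged share q of 40% to 70%, and merging on day 0. The share of patients with an event outside active collection is q × p, from 0.40 × 0.05 = 2% to 0.70 × 0.20 = 14%. This is an upper figure for what goes unrecorded, since it includes related events that remain reportable. With equal shares and risks the between-arm difference is 0. With shares of 70% and 40% it is 0.30 × p, or 1.5 to 6 points, and its sign depends on which arm has the larger share.

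**The case against.** The best defence is that the footnote opens by fixing safety follow-up at 28 ±14 days, and that the synopsis repeats this for both phases without any exception. On that reading a combined visit is held in the safety window and nothing is lost. The reading is available, and it is the natural one for a patient who stops between clinic visits. But it is not written down, and it fits poorly with the low-toxicity trigger.

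The safeguards are also real. Suspected-related late events remain reportable, ongoing AEs are followed to resolution or stabilization (Section 8.4.3), and patients stay in follow-up to 5 years. They narrow the loss to new events judged unrelated or never detected. They do not restore the dropped laboratory check.

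A reader might infer three stronger things that the documents do not support:

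- **That the footnotes abolish the safety window.** No text says so. Closing at EOT is one compliant reading.
- **That only low-toxicity patients are affected.** The first trigger has no toxicity condition. The second looks only at the last visit.
- **That AEs are undercounted more in the BNT321 arm.** Combination completers finish on antibody alone, and their EOT is not tied to a week number, so a difference is conceivable. But the merge wording is the same in both arms, and no merge rate or rate of Grade 2 or higher toxicity at the last visit is given for either. Table 5 also shows that BNT321 monotherapy was not free of toxicity: ALT increased in 42.7%, AST in 39% and bilirubin in 29.3%, any grade.

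**Conclusion.** The point holds as a gap in the visit rules, and it should be corrected. A site can comply with the protocol and end AE collection at EOT, before day 14, leaving up to 100% of the 28-day treatment-emergent window unobserved. The 100% figure assumes a merge on the day of the last dose, and the loss shrinks as the merged visit moves later. From day 14 onward merging costs no more than the protocol already allows.

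The number of patients affected cannot be derived from the documents; the 2% to 14% range rests wholly on assumed risks and merge shares. The same is true of any between-arm difference, whose size and direction stay open. The disease-free survival analysis is not affected.

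**What to change.** Add one sentence to Table 1 footnote 5, Table 2 footnote 5 and Table 4 footnote 4: a combined visit must take place within the safety follow-up window that the footnote already defines (28 ±14 days after the last dose of the drug it names), and AE/SAE collection stays open until the date of that visit. The rule should be the same in both Phase II arms.

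The toxicity trigger can stay, because once the date is fixed it can no longer shorten collection below the protocol's own window. The anchor dose need not change for this purpose. The difference between the 28-day and 60-day treatment-emergent limits is a separate matter.

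The cost is footnote wording and some delay: for merged visits, EOT items such as the disease assessment or the anti-drug antibody sample may be taken up to 42 days after the last dose. A site that needs those items promptly can keep the two visits separate.
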